3. **Research Plan:** Summarize the study design and research procedures using non-technical language that can be readily understood by someone outside the discipline. **Be sure to distinguish between standard of care vs. research procedures when applicable, and include any flowcharts of visits specifying their individual times and lengths.** Describe the setting in which the research will take place.

1. Study Design and Overview

Ninety treatment seeking men and women with AUD will be recruited to participate in and complete this preliminary study. Participants will be recruited through flyers and advertisements in local newspapers and from community substance abuse treatment facilities. Subjects will participate in an initial screening and intake session to obtain informed consent, followed by physical examination and blood work to determine eligibility. Eligible

participants will be randomly assigned to 2 doses of PREG (300/500 mg/day) vs placebo (PLA) treatment (N=30/group) over 8 weeks. In week 2, AUD patients will participate in a 3day human laboratory study where they will be exposed to three experimental sessions of stress, alcohol cue and neutral-relaxing imagery on separate days (Fox et al.,2007; 2009; Sinha et al., 2008; 2009; 2011). Throughout the study, participants will come twice-weekly to the Yale Stress Center to receive medication, counseling and provide urine samples for UTOX. Women will be enrolled during the mid-luteal phase of the menstrual cycle so that laboratory sessions will be scheduled during the early to mid-follicular phase of the cycle when endogenous sex hormone levels are low prior to ovulation. PREG doses and matching placebo will be obtained by Yale IDS for compounding and dosing to 300mg and 500mg of PREG or PLA. Participants will self-administer study medication on a twice-daily dosing schedule throughout entire study.

Subjects will begin with full respective dose of medication immediately without a titration period, as previous studies with similar doses of pregnenolone up to 500 mg/day at b.i.d. dosing to be well tolerated and with no side effects (Marx et. al., 2009; Marx et al., 2014; Brown et al., 2014; Sripada et al., 2013).

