Reporting of Other Study-Safety Events: The project PI will inform the Data Safety Monitor, the Yale HIC, NIDA project officer and the sponsor promptly of any change in recruitment or other changes in this project that are relevant to safety, as well as any action taken by the Yale HIC as a result of continuing review of this project.

12. Statistical Considerations: Describe the statistical analyses that support the study design. For this preliminary study data we will mostly use descriptive statistics for comparing the medication groups on primary outcome measures and safety measures. Repeated measures ANOVA and mixed model procedures to assess treatment group differences in alcohol craving and stress related arousal (heart rate, blood pressure, HPA and catecholamine responses) during laboratory exposure to stress and drug cues as compared to neutral imagery conditions. Non-parametric tests will be used to assess occurrence of side effects, alcohol use measures, CIWA scores and perceived stress scores during the treatment study phase. The number and type of AE's for the two medication groups will be conducted using t-tests, chisquare tests and ANOVAs as appropriate. Findings will be used to estimate effect sizes for the medication and guide the larger randomized clinical trial in the future.

Primary Outcome Measures during 8 week treatment: The primary outcome measures will be:(1) alcohol use as measured by weekly urine drug screens and self-report of drug use on the Substance Use Calendar, (2) side effects and adverse events as measured by the SAFTEE, and (3) treatment adherence as measured by frequency of attendance for medication selfadministration and attendance for counseling appointments, including missed sessions.

Secondary Outcome Measures: Secondary outcome measures will include alcohol craving scales, alcohol withdrawal assessment using the CIWA, perceived stress scale, the recent stressful life events scale (LES), and the COPE Questionnaire. In addition, other assessments will be used to ensure that medications groups are not different in various measures at baseline and also to assess their role in predicting treatment response. Examples of such

assessments would be demographic measures, depressive and anxiety symptoms, motivation to change and thoughts about abstinence, which are measures that have been found to predict substance abuse treatment outcomes (Hall et al., 1990; 1991; McMahon et al., 1986).

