Thus, mixed linear models will be used to test the hypotheses for each of the specific aims. In each case, Subjects will be treated as a random effect and Sex, Imagery Condition and Timeperiod will be treated as fixed effects. PROC MIXED in the Statistical Analysis System (SAS, version 9.3) will be used to model the experimental effects. Each of the specific aims and hypotheses are listed below. For the treatment section of the study, Cox Proportional Hazards models will be used to ascertain differences in time to relapse between AUD individuals treated with pregnenolone compared with those treated with placebo. We anticipate that pregnenolone-treated individuals will demonstrate a survival function reflecting an increase in number of days to relapse compared to the placebo group.

Specific Aim #1: *To evaluate the safety/tolerability of 300mg and 500 mg/day of PREG vs PLA in AUD individuals. Hypothesis 1: PREG 300 and 500 mg/day will be found to be safe, well-tolerated and with fewer side effects/adverse events as compared to the PLA group. Statistics to test hypothesis 1 will compare safety and adverse events data using percentages of various side effects and number and type of AE's for the three treatment groups by each week in treatment using PROC MIXED procedures in SAS, but also frequencies of overall AEs compared across the 8-week period.*

Specific Aim #2a: To evaluate PREG dose (PLA, 300 and 500 mg/day) effects on ALLO and on provoked cue- and stress induced craving, HPA responses, anxiety/mood and cognitive flexibility in AUD patients.

Hypothesis 2a: Compared to PLA, PREG will dose dependently increase ALLO levels and also decrease stress and cue-induced alcohol craving, anxiety, normalize HPA axis basal and response levels of Cortisol, ACTH and adrenal sensitivity (Cortisol/ACTH ratio) and improve Stroop cognitive flexibility.

Specific Aim #2b: To assess whether PREG-stimulated ALLO levels mediate its effects on provoked craving, anxiety, mood, HPA axis response and cognitive flexibility in the laboratory component. Hypothesis 2b: Compared to PLA, higher ALLO levels in the PREG dose groups will mediate greater reductions in alcohol craving, anxiety, mood, cognitive flexibility and normalizing of HPA axis measures specified in Hypothesis 2a.

Specific Aim #3a: To determine the efficacy of 8-week PREG doses versus PLA treatment on primary alcohol use outcomes, and secondary outcomes including alcohol craving, anxiety and mood.

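### Aim 1 puts weekly adverse-event percentages, counts and types into a linear mixed model, and Section V.12 gives conflicting methods and group counts for the same data

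*Combined protocol and SAP*

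**What the plan says.** Section V.3 (Study Design and Overview) randomises participants to two pregnenolone doses "vs placebo (PLA) treatment (N=30/group) over 8 weeks", so there are three arms and 90 participants. Safety and tolerability is Specific Aim 1, and SAFTEE side effects and adverse events are one of the three primary outcome measures in Section V.12. Hypothesis 1 is directional: it predicts fewer events on pregnenolone than on placebo.

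Section V.12 describes the analysis of these events in two places.

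- **Under Specific Aim #1:** the data are "percentages of various side effects and number and type of AE's", compared among three groups "by each week in treatment using PROC MIXED procedures in SAS, but also frequencies of overall AEs compared across the 8-week period". The paragraph before it states that "mixed linear models will be used to test the hypotheses for each of the specific aims". No link function, binomial or count distribution, or exact method is named.
- **In the opening paragraph:** safety comparisons are to be mostly descriptive. Then "Non-parametric tests will be used to assess occurrence of side effects", and "The number and type of AE's for the two medication groups will be conducted using t-tests, chisquare tests and ANOVAs as appropriate".

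**The concern.** A linear mixed model assumes roughly normal errors with a common variance. Weekly event data in 30 participants per arm are mostly zeros, and the variance of a proportion changes with its mean. An interval for a weekly percentage can then run below zero and stop short at the top. In a safety analysis the upper limit is the informative one. The type of event is a category, and a linear model cannot analyse it.

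The two descriptions also disagree. One endpoint is given non-parametric tests, a choice among t-tests, chi-square tests and ANOVA with no rule for choosing, and PROC MIXED. One description counts two groups and the other three. The shorter count may be left over from a two-arm design, or may mean the two active doses without placebo; the text does not settle it. If placebo were left out, Hypothesis 1 would not be tested. At stake are the error bars and week-by-week comparisons for a primary outcome that is meant to guide a larger trial.

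**Working it through.** **Inputs.** From the documents: 3 arms of 30 (Section V.3) and weekly event assessment (Safety and Side Effects Measures). Taking one record per week for 8 weeks gives 3 x 30 x 8 = 720 records. The documents give no expected event rate, alpha or power, so there is no figure of theirs to reproduce. Assumed: two-sided 5%, and weekly rates of 0.5% to 10% per event. With independent weeks, the chance of at least one event in 8 weeks is 1 - (1 - p)^8: 3.9% at p = 0.5%, 7.7% at 1% and 57% at 10%.

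**1. Interval for one event in 30.**
- Normal theory: p = 1/30 = 0.0333; standard error = sqrt(p(1 - p)/29) = 0.0333; t(29) = 2.045. The interval is 0.0333 +/- 2.045 x 0.0333 = **-3.5% to 10.2%**.
- Exact (Clopper-Pearson): **0.1% to 17.2%**.
- For 0/30 the normal-theory interval from that arm alone has zero width. The exact upper limit is 1 - 0.025^(1/30) = 11.6%.

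**2. Null behaviour of the weekly model.** 20,000 simulated trials per setting, no dropout, participant SD on the logit scale 0 or 2, Gaussian repeated-measures analysis with common variance. Ranges cover the two SDs. Empty cells are (1 - p)^30.

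| Weekly rate | Empty arm-week cells | Arm F test rejects | Arm-by-week F rejects | Single-week two-arm contrast rejects | Weekly lower limit below 0 | Coverage of weekly mean |
|---|---|---|---|---|---|---|
| 0.5% | 86% | 2.3-3.4% | 2.9-3.4% | 9.5-9.8% | 84-85% | 87-89% |
| 1% | 74% | 2.7-3.7% | 3.6-4.2% | 6.6-6.9% | 88-89% | 95% |
| 2% | 54.5% | 3.1-4.7% | 4.1-4.4% | 5.1-5.4% | 88% | 96% |
| 5% | 21.5% | 4.0-4.8% | 4.4-4.9% | 4.6-5.2% | 79-80% | 95-96% |
| 10% | 4.2% | 4.4-5.2% | 5.0-5.2% | 5.0-5.2% | 60-63% | 95-97% |

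Simulation error at 5% is about sqrt(0.05 x 0.95/20,000) = 0.15 percentage points.

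**3. Why single-week contrasts over-reject when events are rare.** The contrast is significant when the difference in events exceeds 30 x 1.96 x sqrt(2 s²/30), where s² is the pooled variance. With k events in separate arm-week cells, s² = k x (29/30)/(24 x 29) = k/720. For k = 3 the threshold is 1.96 x sqrt(2 x 30 x 3/720) = 1.96 x 0.5 = 0.98 events, so one event against none in a single week is declared significant. For k = 4 it is 1.96 x sqrt(0.333) = 1.13, and one against none is not. At a weekly rate of 0.5% the expected total is 720 x 0.005 = 3.6 events, so this situation is common.

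**4. Unequal rates under a common variance (independent weeks).**

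| Weekly rates, arms A / B / C | Coverage of B - A | Rejection of C - A (no true difference) |
|---|---|---|
| 1% / 5% / 1% | 91.0% | 0.34% |
| 1% / 10% / 1% | 90.5% | 0.03% |
| 2% / 10% / 2% | 91.8% | 0.40% |

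The interval is too narrow where the arms differ, and the test is far too conservative where they do not.

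**5. Participant-level tests, 30 against 30.** Enumerating all tables for any-event rates of 1% to 30%, the true size of the t-test is 0.03% to 5.4%, the same as uncorrected chi-square. Fisher's test has size 0.0% to 2.6%.

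**The case against.** The strongest defence is that the plan is wider than a linear model. Section V.12 says safety comparisons will be mostly descriptive, names non-parametric and chi-square tests, and adds overall frequencies. Safety review also rests with the data safety monitoring board (Section V.11), not on these p-values. All of this stands, and it limits the severity. It does not supply an interval method or say which of the named tests applies, and Hypothesis 1 is still assigned to PROC MIXED.

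A reader might infer that the p-values are wrong in general. The documents and the checks do not support that: the overall F tests and participant-level t-tests hold their level or fall below it. Single tables can look alarming. For 0/30 against 4/30 the t-test gives 0.039 and Fisher's test 0.112; for 1/30 against 6/30 they give 0.045 and 0.103. But uncorrected chi-square, already in the plan, gives 0.038 and 0.044, so normal errors are not the cause, and Fisher's test is itself conservative. Boschloo's unconditional test (the maximum, over a common event rate, of the probability of a Fisher p-value no larger than the one observed) gives 0.070 and 0.056, much closer to the t-test.

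A reader might also infer that the doses will be pooled against placebo. Neither description says so, and the Aim 1 text names three groups. The effect of pooling would depend on assumed rates. With 5% on placebo and 300 mg and 25% on 500 mg, Fisher power is 44% for 500 mg against placebo and 19% pooled. With 25% on both doses, pooling raises power to 65%. These figures cannot be held against the plan.

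Finally, rarity is an assumption. Side effects asked about at every visit could be common, and at 10% per week the null error rates are close to nominal.

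**Conclusion.** The point holds in limited form. The only model assigned to Aim 1 does not suit binary, count or categorical event data, and Section V.12 is inconsistent about both the test and the number of groups. The damage is in the error bars and single-week contrasts. For 1/30 the upper limit is put at 10.2% when the exact limit is 17.2%. Model-based weekly lower limits are negative in 60% to 89% of simulated trials. Single-week contrasts reject 6.6% to 9.8% of the time at weekly rates of 1% or less, and coverage of a true difference is about 90% to 92%.

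The simulated figures rest on assumed event rates, no dropout and a common-variance model; the plan states no covariance structure for this analysis. The 1/30 intervals and the contradiction in group count need none of these assumptions. The change should be made because this is a primary outcome, but it is moderate in weight because the study is preliminary and mostly descriptive.

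**What to change.** Replace the two descriptions in Section V.12 with one, covering all three arms.

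- **Main analysis:** the number and percentage of participants with at least one event, overall and by event type, in each arm with exact or score 95% intervals. Compare each dose with placebo by an exact test, with a score interval for the difference. An unconditional test such as Boschloo's is less conservative than Fisher's.
- **Weekly data:** where events allow, a logistic GEE or PROC GLIMMIX model for yes/no data and a negative binomial model for counts, in place of PROC MIXED. Fall back on descriptive or exact reporting when cells are empty.
- **Wording:** reconcile the reference to two groups with the three randomised arms, and remove the open choice among tests.

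The cost is a text change in the plan, a little more programming in the same software, and slightly more conservative tests. No new data are needed.

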A Systematic Assessment of Treatment Emergent Events (SAFTEE) will be assessed at each visit to assess any adverse events of side effects that may have occurred in patients during the treatment study. The scale will assess physical or health problems since the last visit, including changes in physical appearance and changes in functioning due to physical condition. If the subject describes any changes a detailed assessment of the symptom or complaint will be conducted using the SAFTEE form pages 2-4. An adverse events form developed by our group will be completed for the event according to the criteria outlined in the Data Safety Monitoring Plan in the Human Subjects section. Thus, study staff and investigators will evaluate all adverse events, and an adverse event report will be completed and the Yale HIC and the Data Safety Monitor will be notified (see Data Safety Monitoring Plan for procedures for safety monitoring and reporting of adverse events). Adverse events/side effects will be assessed weekly throughout the study.

Other Relevant Measures:

QMI Vividness of Imagery Scale (Sheehan, 1967) will be used to assess the vividness of mental imagery. The 35 items of the QMI are statements regarding the imagery ability in seven different sensory modalities (visual, auditory, olfactory, cutaneous, kinaesthetic, gustatory, and organic). Subjects are asked to rate their imagery vividness on a 7-point scale (1 = I perceive it perfectly clearly, as if it were real; 7 = I think about it, but I cannot imagine it). A low score on the QMI indicates more vivid imagery.

The Menstrual Cycle Questionnaire (MCQ) is a 30-item standardized instrument including 23 questions about symptoms experienced during a typical menstrual cycle and questions regarding typical cycle and period length. Female subjects will complete the questionnaire at baseline.

4. Genetic Testing N/A

A. Describe

- i. the types of future research to be conducted using the materials, specifying if immortalization of cell lines, whole exome or genome sequencing, genome wide association studies, or animal studies are planned

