If a subject decides to not continue with the treatment phase, twice-weekly follow-up appointments for one week will be scheduled after the laboratory sessions are complete. They will receive \$25 for each visit. Therefore, if subjects only complete the laboratory phase with the follow up visits and smartphone monitoring, the maximum total payment will be \$490.

3. Costs for Participation (Economic Considerations): Clearly describe the subject's costs associated with participation in the research, and the interventions or procedures of the study that will be provided at no cost to subjects.

There will be no costs charged to subjects who participate in this study. All evaluations including interviews, physical exams, diagnostic tests will be provided at no cost to the subjects.

4. **In Case of Injury:** This section is required for any research involving more than minimal risk.

- a. Will medical treatment be available if research-related injury occurs?
- b. Where and from whom may treatment be obtained?
- c. Are there any limits to the treatment being provided?
- d. Who will pay for this treatment?
- e. How will the medical treatment be accessed by subjects?

While medical therapy will be offered for any physical injuries sustained as a consequence of participation in this research, the subject and their insurance carrier will be responsible for the cost of such treatment. Financial compensation for injury is not available.

REFERENCES

Beck, A., C. Ward, et al., (1961). "An inventory for measuring depression." *Archives of General Psychiatry* 4: 461-471.

Bradley, B. P., Phillips, G., Green, L., Gossop, M., (1989). "Circumstances surrounding the initial lapse to opiate use following detoxification." *Br. J. Psychiatry.* 154, 354-359.

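### Adverse events are compared as crude 8-week frequencies with no allowance for observation time, although participants who stop after the laboratory phase have scheduled visits only to about week 3

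*Combined protocol and SAP*

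**What the plan says.** Section V.12 lists three primary outcome measures, and one of them is "side effects and adverse events as measured by the SAFTEE". AEs are also the subject of Specific Aim 1, where Hypothesis 1 expects both doses to be well tolerated, "with fewer side effects/adverse events as compared to the PLA group".

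The Specific Aim #1 paragraph plans two comparisons. The first takes percentages, number and type of events "for the three treatment groups by each week in treatment using PROC MIXED procedures in SAS". The second is "but also frequencies of overall AEs compared across the 8-week period". The opening paragraph of Section V.12 describes the AE analysis again: "The number and type of AE's for the two medication groups will be conducted using t-tests, chisquare tests and ANOVAs as appropriate". None of this text gives person-time, an exposure offset, a censoring rule or the denominator of the weekly percentages.

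On observation, the design in Section V.3 (Study Design and Overview) is two doses "vs placebo (PLA) treatment (N=30/group) over 8 weeks", with the laboratory sessions in week 2. For a participant who does not go on to the treatment phase, Section X.2 says that "twice-weekly follow-up appointments for one week will be scheduled after the laboratory sessions are complete". Under Safety and Side Effects Measures in Section V.3, the SAFTEE "will be assessed at each visit to assess any adverse events of side effects that may have occurred in patients".

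**The concern.** The design itself creates two lengths of observation: 8 weeks for those who continue and about 3 weeks for those who stop after the laboratory phase. If AEs are counted per arm over 8 weeks and divided by the number randomised, the weeks in which nobody was looking count as event-free. Two arms with the same true rate can then show different frequencies simply because more people left one of them.

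The outcome is a listed primary, and the results are meant to guide a larger trial. A lower AE frequency on pregnenolone could not be told apart from shorter observation, and a real excess could be hidden.

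**Working it through.** The plan states no AE rate, dropout rate or power for this outcome, so there is no figure of its own to reproduce.

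**Inputs from the document**
- 30 per arm, 8 weeks, laboratory sessions in week 2 (Section V.3).
- One further week of visits for those who stop (Section X.2), so about 3 weeks in all.
- 92% completion in earlier stress studies, so 8% non-completion (Section V.3, retention paragraph).

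**Assumptions**
- A share d of an arm leaves at week 3, with d from 8% to 40%.
- Where a rate is needed, 0.10 AEs per person-week.

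**1. Observed time.** Person-weeks per participant = 8(1 − d) + 3d. With the same constant rate in every arm, the count ratio against the 8% arm is the ratio of person-weeks.

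| d | Person-weeks | Count ratio vs 8% arm |
|---|---|---|
| 8% | 7.36 + 0.24 = 7.6 | 1.00 |
| 20% | 6.4 + 0.6 = 7.0 | 7.0/7.6 = 0.92 |
| 30% | 5.6 + 0.9 = 6.5 | 6.5/7.6 = 0.86 |
| 40% | 4.8 + 1.2 = 6.0 | 6.0/7.6 = 0.79 |

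Read the other way, a true excess of 7.6/6.5 = 1.17 (30% leaving) or 7.6/6.0 = 1.27 (40% leaving) would appear as no difference.

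**2. At the document's own figure.** If one arm loses 8% and the other none, the ratio is 7.6/8.0 = 0.95, a 5% distortion. This takes 8% as the rate within an arm. If 8% of all 90 participants left (7.2 people) and every one came from a single arm of 30, that arm would lose 24% and the ratio would be (8 − 5 × 0.24)/8 = 6.8/8.0 = 0.85. That is an extreme allocation, and nothing in the document suggests it.

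**3. Percentage with any AE.** Share = (1 − d)(1 − e^(−8r)) + d(1 − e^(−3r)). At r = 0.10 it is 52.7%, 46.3% and 43.4% for d = 8%, 30% and 40%.

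**4. AEs that come early.** If a share f of all 8-week AEs falls in weeks 1–3, counts are proportional to (1 − d) + df. With f = 0.8, the ratio of 40% against 8% leaving is 0.920/0.984 = 0.935. With f = 1 it is 1.00.

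**5. AEs that cause leaving.** If leavers have k times the weekly rate before they go, counts are proportional to 8(1 − d) + 3kd. At k = 8/3 the count ratio is 1.00 for every d. At k = 4, with 40% against 8% leaving, it is 9.6/8.32 = 1.15.

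**6. After adjustment.** With a common rate of 0.10 and 30 per arm, expected events over person-weeks are 22.8/228, 19.5/195 and 18.0/180 for 8%, 30% and 40% leaving. Each gives 0.10, a rate ratio of 1.00.

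**The case against.** The strongest reply is that the direction of the error is not established. A reader might infer that the arm with more dropout will look safer, and so that the error favours Hypothesis 1. The document does not support that. It would need unequal leaving, AEs that continue past week 3, and leavers without a much higher early AE rate. Steps 4 and 5 show the bias in counts disappearing or reversing when the last two fail. This objection stands. Part of the point survives it: the count ratio always equals the observed rate ratio times the ratio of person-weeks. At k = 8/3 with 40% against 8% leaving, counts are equal (0.80 per participant), yet the observed rates are 0.80/6.0 = 0.133 and 0.80/7.6 = 0.105, a ratio of 1.27.

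A reader might also say that a leaver's AE frequency is understated by 1 − 3/8 = 62.5%. That holds only for counts under a constant rate, not for the percentage with any AE.

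The by-week comparison comes first in the same sentence, and it would largely align exposure if each week's denominator were the participants still observed. That denominator is not given, and the overall comparison stays unadjusted either way.

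Nor is the SAFTEE at visits the only source of AEs. Section V.9 names daily smartphone monitoring as part of safety monitoring, and Section V.3 plans home visits and telephone interviews after missed appointments. Section X.2 concerns payments and does not say that AE collection stops. None of these passages commits the trial to collecting AEs to week 8 from those who stop.

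Finally, this is a small, mostly descriptive preliminary study with board review of all AEs. At 22.8 against 19.5 events, the 95% interval on the ratio spans a factor of exp(1.96 × √(1/22.8 + 1/19.5)) ≈ 1.8 each way, wider than the distortions above. That limits the weight of the point, but a descriptive AE table still needs a stated denominator.

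**Conclusion.** The point holds in conditional form. The overall 8-week AE comparison ignores observation time, while the design gives those who stop after the laboratory phase scheduled visits to about week 3 only. If leaving differs between arms and AEs continue after week 3, the crude comparison understates the AE rate of the less-observed arm.

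The size runs from about 5% (8% leaving in one arm, none in the other) to 8%, 14% and 21% (20%, 30% and 40% leaving against 8%). These figures assume a constant AE rate, the same in leavers and stayers, and place every leaver at week 3. People who leave later would distort the comparison less. The leaving rates above 8% are assumptions.

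The document does not show which arm would benefit, so this is a cheap and worthwhile improvement, not evidence that the safety conclusion is tilted towards the drug.

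**What to change.** In Section V.12, Specific Aim #1:

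- Keep the crude overall frequency. Beside it, report AEs per person-week observed by arm, from a count model with log person-weeks as offset.
- Add time to first AE, censored at the last AE assessment.
- Use the participants actually observed in each week as the denominator of the by-week percentages.
- Report observed weeks and reasons for stopping by arm.
- State whether AEs are collected to week 8 from participants who stop.
- State the limits. The person-week rate assumes a constant rate and can overcorrect if AEs come early; the time-to-event analysis assumes that leaving is uninformative.

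Two inconsistencies need reconciling at the same time. The opening paragraph of Section V.12 refers to two medication groups where Specific Aim #1 has three. The laboratory section of V.3 mentions a 4-week study period where the rest of the plan has 8, and this bears on the AE window.

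The cost is plan wording and a few extra tables, settled before unblinding. The analyses use visit and assessment dates and need no new data. Following leavers to week 8, if chosen, would be a separate operational decision.
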